11.2 Breaking of blinded codes

If the trial site needs to break the code, Novo Nordisk should, if possible, be contacted before the code is broken. The IV/WRS will notify Novo Nordisk (monitor and the Global Safety department) immediately after the code is broken.

The code for a particular subject may be broken in a medical emergency if knowing the actual treatment would influence the treatment of the subject. Whenever a code is broken the person breaking the code must print the Code Break Confirmation Notification generated by the IV/WRS, record the reason, and sign and date the document.

If the subject is withdrawn after the code has been broken, a withdrawal session should be completed in the IV/WRS.

When the code is broken, the treatment allocation will be accessible to the investigator and the Novo Nordisk Global Safety department, and any other relevant party. If the IV/WRS is not accessible at the time of code break the IV/WRS vendor helpdesk should be contacted. Contact details are listed in attachment II.

Key codes will be disclosed to the sponsor after the 1st database lock in this trial to analyse and submit the data from the pivotal phase to the Authority. Even after the key open, investigators, sub-investigators and the subjects will be kept blinded until the 2nd database lock.

12 Adverse events, and technical complaints

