14.1 Medical problem

The investigator should assess whether the medical problem entered into the daily dosage note should be considered an AE. If the medical problem is considered an AE, an AE form must be completed in the CRF, according to section [12.2](#).

15 Data management

Data management is always the responsibility of Novo Nordisk. Data management activities including computer system operations may be delegated under an agreement of transfer of responsibilities to another data management unit within Novo Nordisk.

Laboratory data will be transferred electronically from the central laboratory performing clinical analyses. In the case where laboratory data is transferred via non-secure electronic networks, data will be encrypted during transfer. Details of laboratory data formats and transfer will be specified in a separate written agreement between the laboratories and Novo Nordisk.

The subject and biological material obtained from the subject will be identified by subject ID and trial identification number. Appropriate measures such as encryption or leaving out certain identifiers will be enforced to protect the identity of subjects in all presentations and publications as required by local, regional, and national requirements.

16 Computerised systems

Novo Nordisk will capture and process clinical data using computerised systems which are described in Novo Nordisk standard operating procedures (SOPs) and IT architecture documentation. The use and control of these systems are documented.

The investigators working on the trial may use their own electronic systems to capture source data. Novo Nordisk will collect information on the practical use of these systems within the conduct of this clinical trial.

17 Statistical considerations

If necessary, a statistical analysis plan (SAP) may be written in addition to the protocol, including a more technical and detailed elaboration of the statistical analyses. The SAP will in that case be finalised before database lock.

Analyses of all efficacy endpoints will be performed based on the full analysis set (FAS). The primary analysis of the primary endpoint will be repeated on the per protocol (PP) analysis set.

Safety endpoints will be summarised using the safety analysis set (SAS).

The impact of protocol deviations and outliers may be investigated further in sensitivity analyses if deemed relevant.

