1.2 Scope of the statistical analysis plan

This Statistical Analysis Plan (SAP) is based on the statistical analyses of GHLIQUID-4020 as planned in the trial protocol.

Changes to the statistical methods proposed in this SAP and the reason for the change must be reported in the clinical trial report (CTR).

This SAP is based on the protocol version 2.0 (Dated 03 March 2016).

2 Statistical considerations

Analyses of all efficacy endpoints will be performed based on the full analysis set (FAS). The primary analysis of the primary endpoint will be repeated on the per protocol (PP) analysis set.

Safety endpoints will be summarised using the safety analysis set (SAS).

The impact of protocol deviations and outliers may be investigated further in sensitivity analyses if deemed relevant.

Missing values for endpoints other than OGTT, HbA_{1c} and bone age will be imputed using the last observation carried forward (LOCF) method.

All endpoints will be summarised descriptively at each visit by treatment using observed data. After 104 weeks of treatment, descriptive statistics will be presented based on both observed and LOCF imputed data. Endpoints that are analysed untransformed and endpoints that are not formally analysed are summarised by the arithmetic mean, standard deviation (SD), median, and minimum and maximum value. Endpoints that are analysed log-transformed are summarised by the geometric mean, coefficient of variation (CV), median, minimum and maximum value.

LOCF imputed data will be used as the basis for plotting data.

A formal statistical test will only be performed at 104 weeks. Presentation of results from a statistical analysis will include the estimated mean treatment effects (LSMeans). Estimated mean

treatment differences (or ratios) will be presented together with two-sided 95% confidence intervals and p values for all endpoints analysed statistically.

For endpoints measured over time mean values will be plotted to explore the trajectory over time. Data collected before randomisation will only be summarised descriptively.

Statistical analysis will be performed twice, at 104 weeks and at the end of trial including extension phase.

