2.3 Primary endpoint

The primary endpoint is change in height SDS from baseline to 104 weeks of treatment according to the Japanese reference dataⁱⁱ. A height SDS will be also calculated according to the Noonan syndrome reference data in Japaneseⁱⁱⁱ.

Statistical analysis

Since the primary objective of this trial is to evaluate the growth promoting effect of NN-220, the following hypothesis will be statistically tested; $H_0: \mu_1 = \mu_2$ vs. $H_1: \mu_1 \neq \mu_2$, where μ_i is the population mean, $i = 1, 2$ represents 0.033 mg/kg/day and 0.066 mg/kg/day, respectively. Primary analysis for the primary endpoint will be performed based on the ANCOVA model with treatment as a fixed effect and baseline height SDS as a covariate.

Sensitivity analysis

The same analysis as for the primary endpoint will be repeated on the PP analysis set.

All height SDS measurements at scheduled time points after randomisation will be analysed in a linear mixed model with treatment, time and interaction between treatment and time as fixed effects, baseline height SDS and interaction between baseline and time as a covariate and subject as a random effect. This approach assumes that data are missing at random according to the taxonomy defined by Rubin (1976)^{iv}. Treatment differences at 104 weeks will be estimated using this model.

Any marked difference concerning treatment differences between the sensitivity results and the result from the primary endpoint will be commented upon in the CTR.

Exploratory analysis

In order to investigate effects of sex, age at start of treatment and baseline height SDS on the primary endpoint, change in height SDS from baseline to 104 weeks of treatment will be analysed based on the ANCOVA model with treatment and sex as fixed effects and age at start of treatment and baseline height SDS as covariates. Parameter estimates for sex, age at start of treatment and baseline height SDS will be presented together with two-sided 95% CIs and p values.

Height SDS (Noonan syndrome reference data in Japanese)

In addition to height SDS according to the Japanese reference data, height SDS will be also calculated according to the Noonan syndrome reference data in Japanese. The change in height SDS (Noonan syndrome reference data in Japanese) from baseline to 104 weeks of treatment will be

analysed based on the ANCOVA model with treatment as a fixed effect and baseline height SDS (Noonan syndrome reference data in Japanese) as a covariate.

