2.4.3 Endpoints for the whole trial including the extension phase

The period of the extension phase is 104 weeks, and the period of the whole trial will be 208 weeks [104 weeks in the pivotal phase and 104 weeks in the extension phase]. However, if the indication has not yet been approved or rejected by the PMDA at 208 weeks for the first subject, the period for the extension phase will be extended for at least 26 weeks (6 months).

The endpoints at 208 weeks for the whole trial including the extension phase are defined in the same way as for the pivotal phase.

All efficacy and safety endpoints and parameters will be summarised and analysed in the same way as for the 104 weeks.

TEAEs will be defined as an event that has onset date on or after the first day of exposure to NN-220 and no later than 7 days after the last day of NN-220 treatment.

3 Changes to the statistical analyses planned in the protocol

The following changes from the protocol are implemented in this SAP

Terminology

“Efficacy parameters” is changed to “secondary efficacy endpoints” in section 4.2 in the protocol version 2 but it is not reflected to the section 17. In this SAP, it is changed to “secondary efficacy endpoints” from “efficacy parameters”.

Exploratory analysis on the primary endpoint

In order to investigate effects of sex, age at start of treatment and baseline height SDS on the primary endpoint, change in height SDS from baseline to 104 weeks of treatment is analysed based on the ANCOVA model with treatment and sex as fixed effects and age at start of treatment and baseline height SDS as covariates.

Statistical analysis of height SDS according to the Noonan reference

A statistical analysis on change from height SDS according to the Noonan reference in the protocol is included.

Derivation of AUC

Imputation of missing data for each individual profile is specified.

Definition of treatment emergent adverse event

The date of visit 2 (0 week) instead of the first day of exposure to NN-220 is used for a definition of a treatment emergent adverse event since the first day of exposure to NN-220 is not available in the database by the end of treatment.

Treatment emergent adverse event based on pre-defined MedDRA search

Summary tables based on system organ class and preferred term are made for treatment emergent adverse event based on pre-defined MedDRA search.

4 References

-

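### Does the age- and sex-adjusted dose difference need to be a named sensitivity analysis rather than part of an exploratory model?

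*SAP*

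**What the plan says.** SAP section 2.3 sets out three layers of analysis for the change in height SDS to 104 weeks.

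- **Primary:** "Primary analysis for the primary endpoint will be performed based on the ANCOVA model with treatment as a fixed effect and baseline height SDS" as the covariate. Protocol section 17.3 specifies the same model.
- **Sensitivity:** a repeat of the primary ANCOVA on the per-protocol set, and a linear mixed model on all scheduled post-randomisation measurements. The subsection ends: "Any marked difference concerning treatment differences between the sensitivity results and the result from the primary endpoint will be commented upon in the CTR".
- **Exploratory:** "the ANCOVA model with treatment and sex as fixed effects and age at start of treatment and baseline height SDS as covariates". The stated aim is to investigate the effects of sex, age and baseline height SDS on the endpoint, and the output sentence is "Parameter estimates for sex, age at start of treatment and baseline height SDS will be presented together with two-sided 95% CIs and p values".

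SAP section 3 lists the exploratory model among the additions to the protocol, under an exploratory heading: "change in height SDS from baseline to 104 weeks of treatment is analysed based on the ANCOVA model", with the same four terms.

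SAP section 2 holds rules that apply throughout. Efficacy analyses use the full analysis set. Missing values are carried forward, except for OGTT, HbA1c and bone age. Results from a statistical analysis include the least-squares treatment means. Estimated "treatment differences (or ratios) will be presented together with two-sided 95% confidence intervals and p values for all endpoints analysed statistically".

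On timing, protocol section 17 says of any SAP: "The SAP will in that case be finalised before database lock". Protocol section 11.2 says: "Key codes will be disclosed to the sponsor after the 1st database lock".

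**The concern.** Neither the primary model nor either sensitivity analysis adjusts for age or sex. Boys may enter from 3 to under 11 years and girls from 3 to under 10 (protocol 6.2). Protocol 11.1 describes 1:1 allocation and names no stratification factor, although part of protocol section 10, on the IV/WRS, is missing from the available text. With 24 children per arm, chance differences in mean age are to be expected, and a reader may well ask whether the dose difference survives adjustment.

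The model that answers this is in the SAP, yet its named outputs are the three covariate estimates and not the dose difference. Because the model is headed exploratory, the duty to comment on marked differences does not reach it. Read strictly, the trial report could omit the adjusted dose difference, or show it without comment even if it departed from the primary result. At stake would be the reader's ability to judge how far the primary estimate depends on the choice of covariates.

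**Working it through.** **1. The plan's own figure.** Protocol 17.1 uses a two-sided 5% two-sample t-test, difference 0.45, SD 0.5 and 80% power. The exact noncentral-t calculation gives 79.2% power with 20 per group and 81.2% with 21, so 21 reproduces. Allowing for 10% withdrawal, 21 / 0.9 = 23.3, rounded up to 24 per group and 48 in total. The concern disputes none of these figures.

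**2. What is already fixed for the adjusted model.**

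| Element | Where it is settled |
|---|---|
| Model terms | SAP 2.3, repeated in SAP 3 |
| Analysis set (FAS) | SAP 2, efficacy analyses |
| Missing values (LOCF) | SAP 2, general rule |
| Treatment means from the model | SAP 2, rule for statistical analyses |
| Treatment difference with CI and p value | SAP 2, worded per endpoint, so open to two readings |
| Covariate estimates with CI and p value | SAP 2.3 |
| Sensitivity status, duty to comment | Not given |

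The model contains treatment and analyses the primary endpoint, so the rule on treatment means covers it on a natural reading. The three covariate estimates in SAP 2.3 then read as an addition to that rule, needed because the general rule does not mention covariates. The last row is the only element that is plainly absent.

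**3. Precision with and without age and sex.** Assumptions: N = 48, SD 0.5 after baseline adjustment, and R² for the share of the remaining variance that age and sex explain. The documents give no R², so a range is used. With k covariates,

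half-width = t(0.975, N − 2 − k) × 0.5 × √(1 − R²) × E[(1 − q)^−½] / √(N/4),

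where q ~ Beta(k/2, (N − 1 − k)/2) is the chance R² of treatment on the covariates.

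- Baseline only (k = 1): 2.014 × 0.5 × 1.011 / √12 = 0.294.
- Age and sex added (k = 3), R² = 0: 2.017 × 0.5 × 1.035 / √12 = 0.301.

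| R² | Half-width, k = 3 (SDS) | Ratio to 0.294 |
|---|---|---|
| 0 | 0.301 | 1.025 |
| 0.05 | 0.294 | 0.999 |
| 0.10 | 0.286 | 0.972 |
| 0.20 | 0.269 | 0.916 |
| 0.30 | 0.252 | 0.857 |

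The two models break even at R² = 0.047.

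**4. How far the two estimates differ by chance.** Both ANCOVAs were fitted to the same simulated trials, 20,000 for each R². Assumptions: true difference 0.45, 24 per arm by simple permutation, equal numbers of boys and girls, age uniform over the entry range, baseline independent of age and sex, and the explained variance carried by age. The mean gap between the estimates was within 0.0003 of zero, as randomisation requires.

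| R² | Median absolute gap (SDS) | 95th percentile (SDS) | Correlation |
|---|---|---|---|
| 0 | 0.015 | 0.067 | 0.98 |
| 0.05 | 0.024 | 0.096 | 0.95 |
| 0.10 | 0.031 | 0.114 | 0.93 |
| 0.20 | 0.043 | 0.144 | 0.88 |
| 0.30 | 0.054 | 0.171 | 0.82 |

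The largest of these, 0.171, is 38% of the planned difference (0.171 / 0.45) and 58% of the primary half-width (0.171 / 0.294). In these simulations a gap of that size is chance, and the primary interval already allows for chance imbalance.

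**5. What a change of heading would alter.** Moving the adjusted dose difference under the sensitivity heading leaves the primary model, test, alpha, N and missing-value rule untouched. It adds a duty to comment on an undefined marked difference, where gaps of up to about 0.07 to 0.17 SDS are expected by chance in 95% of trials. It does not bring the precision gain in step 3 to the primary result, because the primary model stays as it is.

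**The case for a change.** The strongest case for the concern is textual, and its reading is accurate. The adjusted dose difference is not named as an output. The rule on differences with CIs and p values is worded per endpoint, so the primary model alone could satisfy it. Even on the generous reading of SAP section 2, nothing requires the adjusted and primary results to be compared. The existing sensitivity analyses vary the analysis set and the missing-data assumption, not the covariates. The remedy would be one sentence, and status assigned before the sponsor receives the codes cannot later be called result-driven.

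What stands is the missing sensitivity status, with the duty to comment that would follow from it. The rest has less weight:

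- The timing argument matters most when the model could be chosen after seeing the data. Here the terms are written down, and protocol section 17 requires the SAP to be final before database lock. SAP 1.2 also requires changes to its methods to be reported with reasons, so the model could not simply be dropped.
- The exploratory heading fits the stated purpose, which is to describe covariate effects. Adding prognostic covariates in a randomised trial tests neither of the assumptions that the two sensitivity analyses examine. Where to file the model is a matter of preference.
- The endpoint and its baseline covariate are standard deviation scores from Japanese reference data, and protocol 6.2 describes height SDS as relative to chronological age. Height is therefore already scaled for age. A response to treatment that varies with age remains possible, but the documents give no figure for it.

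**Conclusion.** The concern does not hold. A report that follows the SAP as written gives a valid, unbiased dose difference with an interval that already allows for chance imbalance in age and sex, alongside a pre-specified model containing both. The residue is a heading and a duty to comment, and supplying them would change no primary result.

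In size, the two models' 95% CI half-widths differ by between 2.5% wider and 14.3% narrower for the adjusted one, and their estimates lie within 0.067 to 0.171 SDS of each other in 95% of trials. These figures assume 24 per arm, SD 0.5 after baseline adjustment, a true difference of 0.45 and an R² for age and sex between 0 and 0.30. The R² is not in the documents. The conclusion does not depend on it, since under randomisation both estimates are unbiased whatever its value.

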2.4 Secondary endpoints

2.4.1 Efficacy endpoints

Secondary efficacy endpoints are as follows.

- Height velocity SDS from baseline to 52 weeks of treatment^v
- Height velocity SDS from 52 weeks to 104 weeks of treatment
- Height velocity from baseline to 52 weeks of treatment
- Height velocity from 52 weeks to 104 weeks of treatment

Statistical analysis

Secondary efficacy endpoints will be summarised and graphically presented.

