8.1.4.3 Withdrawn subjects

Subjects randomised in error must be withdrawn from the trial.

If a subject is withdrawn from the trial,

- the investigator must aim to undertake procedures similar to those for Visit 20 as soon as possible.

- although a subject is not obliged to give his/her reasons for withdrawing from the trial, the investigator should make a reasonable effort to ascertain the reason, while fully respecting the subject's rights. Where the reasons are obtained, the primary reason (AE, non-compliance with the protocol, withdrawal criteria or others) for discontinuation must be specified in the CRF.
- a withdrawal session must be performed using the IV/WRS.
- the end of trial form must be completed, and final drug accountability of trial products must be performed even if the subject is not able to come to the site.

8.1.5 Visit 20

Please see flow chart (section [2](#)) and assessment sections (sections [8.2](#), [8.3](#), [8.4](#), [8.5](#) and [8.6](#))

The subjects must attend fasting, having consumed only water from 9 pm the previous evening.

Subjects will be asked to bring all empty, partly used and unused trial products for drug accountability of trial products.

Drug accountability should be performed using the IV/WRS drug accountability module to confirm allocated, returned and lost pen devices.

The subject completion should be registered in the IV/WRS by performing a completion session.

The investigator will complete an end of trial form.

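### LOCF is not switched off for the four height-velocity endpoints, which have no stated derivation, and carrying forward does not give a sensible growth rate for children who leave early

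*SAP*

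**What the plan says.** The general rule in SAP section 2 (Statistical considerations) is: "Missing values for endpoints other than OGTT, HbA_{1c} and bone age will be imputed using the last observation carried forward (LOCF) method". Protocol section 17 has the same rule.

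SAP 2.4.1 lists height velocity and height velocity SDS, each for weeks 0-52 and weeks 52-104, for example "Height velocity from 52 weeks to 104 weeks of treatment" and "Height velocity SDS from 52 weeks to 104 weeks of treatment". Their analysis is one sentence: "Secondary efficacy endpoints will be summarised and graphically presented".

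Two further sentences in SAP section 2 fix which data are shown. For tables: "After 104 weeks of treatment, descriptive statistics will be presented based on both observed and LOCF imputed data". For figures: "LOCF imputed data will be used as the basis for plotting data".

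Efficacy is analysed on all randomised children, so early leavers count. Protocol 8.1.4.3 asks that on withdrawal "the investigator must aim to undertake procedures similar to those for Visit 20 as soon as possible". Visit 20 includes height, so there will usually be a last height to carry.

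Neither document gives a velocity formula. Neither says whether LOCF acts on height or on velocity, or whether the divisor is nominal or actual time. The changes listed in SAP section 3 do not exempt velocity.

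**The concern.** LOCF fills a missing level with an earlier level. A velocity is a difference between two levels divided by time. Carrying one of the two heights forward removes growth from the numerator, and carrying the velocity moves a rate from one year into another. First-year and second-year velocity are separate endpoints because the response to growth hormone is expected to change over time, so that substitution is not neutral.

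The bone-age endpoints, which are exempt, include a comparable rate: the yearly ratio of change in bone age to change in chronological age. The documents give no reason for exempting that rate and not height velocity.

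What is at stake is how the velocity results look. Two programmers could both follow the SAP and produce different LOCF tables and different figures. No observed-data version of the figures is planned.

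**Working it through.** **Inputs**
- LOCF scope, plot basis and endpoint list: SAP sections 2 and 2.4.1.
- Withdrawal of 10% and 24 children per arm: Protocol 17.1.
- Withdrawal of 6.1% and 5.9% in the earlier trial in children born small for gestational age: Protocol 17.1.
- Assumed, not in the documents: the illustrative growth rates, the even spread of withdrawals, and the velocity mean and SD in step 4.

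**1. The plan's own figure.** The documents give no velocity result under LOCF, so there is none to reproduce. The withdrawal allowance used below does reproduce: 21 / (1 - 0.10) = 23.3, rounded up to 24 per arm.

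**2. One child under each reading.** Assume steady growth of 8 cm/year in year 1 and 6.5 cm/year in year 2, with a height taken on leaving.

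| Leaves at week | Height carried, nominal weeks: year 1 | Height carried, nominal weeks: year 2 | Height carried, actual dates: year 2 | Velocity carried: year 2 |
|---|---|---|---|---|
| 26 | 8 x 26/52 = 4.0 | 0 | 0/0 | nothing to carry |
| 39 | 8 x 39/52 = 6.0 | 0 | 0/0 | nothing to carry |
| 65 | 8.0 | 6.5 x 13/52 = 1.625 | 6.5 | 8.0 |
| 78 | 8.0 | 6.5 x 26/52 = 3.25 | 6.5 | 8.0 |
| 91 | 8.0 | 6.5 x 39/52 = 4.875 | 6.5 | 8.0 |

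The true second-year rate is 6.5. The nominal-week reading is wrong for every leaver. The actual-date reading gives the right rate for later leavers here, but only by measuring over a shorter interval, and it is undefined for leavers before week 52. The velocity-carried reading reports the first-year rate as the second-year rate.

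**3. Average effect on the nominal-week reading.** Spread leaving times evenly over weeks 0-104, and assume leavers grow at the same rate as those who stay.
- Second year: half the leavers keep 0 of their velocity and the other half keep 50% on average. Share kept = 0.5 x 0 + 0.5 x 0.5 = 0.25. Loss in the arm mean = 10% x 0.75 = 7.5%.
- First year: half keep 50% on average and half keep all. Share kept = 0.5 x 0.5 + 0.5 x 1 = 0.75. Loss = 10% x 0.25 = 2.5%.
- Expected leavers before week 52: 24 x 0.10 x 0.5 = 1.2 per arm. At the earlier trial's roughly 6%: 24 x 0.06 x 0.5 = 0.7.

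**4. In cm/year.** Assume a second-year mean of 6 (range 5 to 7) and SD of 1.2. One zero among 24 lowers the mean by 6/24 = 0.25 (0.21 to 0.29) and raises the SD to 1.7. Two zeros lower it by 0.50 (0.42 to 0.58) and raise the SD to about 2.05.

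**5. Velocity SDS.** A zero converts to -(reference mean)/(reference SD). Neither value is in the documents. An assumed mean of 5 to 7 with SD of 0.6 to 1.2 gives anything from -5/1.2 = -4.2 to -7/0.6 = -11.7, which is too wide to size the effect.

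**The case against.** The strongest reply is that the SAP imputes endpoints, and here the endpoint is velocity, not height. Nothing says that height is carried to nominal weeks first. If each velocity is treated as an endpoint measured once, there is nothing to carry and no distortion. This stands as far as it goes. A reader might infer that every child who leaves before week 52 is assigned 0 cm/year and an extreme velocity SDS. The documents do not support that as a certainty: zero follows from one natural reading among several, and the SDS cannot be computed from what they contain. But the harmless reading is not written down either, and the stated rule covers these endpoints by default.

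The second reply is that little depends on it. The velocities are descriptive with no specified test, an observed-data summary accompanies the LOCF one at week 104, and few early leavers are expected. This also stands for the tables. It does not stand for the plots, which rest on LOCF data alone.

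A reader might also infer a spurious dose difference worth a large part of the 1.9 cm/year (5.4 minus 3.5) that can be taken from Protocol 5.4. That would need about two early leavers in one arm and none in the other, against about 1.2 per arm expected at 10%. The 1.9 also compares changes in height velocity and is not tied to weeks 52-104, so it is not a like-for-like yardstick.

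**Conclusion.** The point holds as a flaw in the imputation rule with limited reach. LOCF covers the four velocity endpoints, their derivation is undefined, and applying LOCF gives a wrong, undefined or misplaced second-year rate for some or all leavers, depending on the reading.

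On the height-carried, nominal-week reading the loss is about 7.5% of mean velocity for weeks 52-104 and 2.5% for weeks 0-52. This assumes 10% withdrawal spread evenly, a height at leaving, and leavers growing like the rest. The effect on velocity SDS cannot be sized.

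The damage is confined to the descriptive week-104 LOCF summary and the velocity plots. The primary ANCOVA and the sample size are not affected. It should be corrected because the change is small and the plots have no observed-data counterpart.

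**What to change.** In SAP section 2, add height velocity and height velocity SDS to the endpoints exempt from LOCF. In SAP 2.4.1, state that each velocity is derived only when both bounding heights are observed (baseline and week 52, or week 52 and week 104), as the height difference divided by the actual elapsed time. Actual time matters even for completers: with windows of ±14 days at weeks 52 and 104, the interval can differ from 52 weeks by up to 4 weeks, or 4/52 = 7.7%. Base the velocity plots on observed data. Apply the same rule at 208 weeks, since SAP 2.4.3 repeats the week-104 approach.

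The cost is a few lines of SAP text. The small downside is that a child who leaves before an interval ends contributes no velocity for that interval. At 10% withdrawal spread evenly, that is about 1.2 of 24 per arm for the first year and 2.4 of 24 for the second, so the number of children should be shown with each summary.
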